4.6.2 Nivolumab Dose Delay Criteria

Nivolumab administration should be delayed for the following:

- Grade 2 non-skin, drug-related adverse event, with the exception of fatigue
- Grade 2 drug-related creatinine, AST, ALT and/or Total Bilirubin abnormalities
- Grade 3 skin, drug-related adverse event
- Grade 3 drug-related laboratory abnormality, with the following exceptions
- Grade 3 lymphopenia or asymptomatic amylase or lipase does not require dose delay
- Grade ≥ 3 AST, ALT, total bilirubin will require dose discontinuation
- Any adverse event, laboratory abnormality, or intercurrent illness which, in the judgment of the investigator, warrants delaying the dose of study medication

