4.6.4 Criteria to Resume Treatment with Nivolumab

Subjects may resume treatment with nivolumab when the drug-related AE(s) resolve to Grade \leq 1 or baseline value, with the following exceptions:

- Subjects may resume treatment in the presence of Grade 2 fatigue
- Subjects who have not experienced a Grade 3 drug-related skin AE may resume treatment in the presence of Grade 2 skin toxicity
- Subjects with Grade 2 AST, ALT and/or Total Bilirubin Abnormalities, dosing may resume when laboratory values return to baseline and management with corticosteroids, if needed, is complete.
- Drug-related pulmonary toxicity, diarrhea, or colitis must have resolved to baseline before treatment is resumed. Subjects with persistent Grade 1 pneumonitis after completion of a steroid taper over at least 1 month may be eligible for re-initiation of treatment if discussed with and approved by the BMS Medical Monitor.

Participants with drug-related endocrinopathies adequately controlled with only physiologic hormone replacement may resume treatment after consultation with the BMS Medical Monitor (or designee). Adrenal insufficiency requires discontinuation regardless of control with hormone replacement.

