4.6.5.1 Nivolumab Dose Discontinuation

- Any Grade 2 drug-related uveitis or eye pain or blurred vision that does not respond to topical therapy and does not improve to Grade 1 severity within the re-initiation period OR requires systemic treatment
- Any Grade 3 non-skin, drug-related adverse event lasting > 7 days, with the following exceptions for laboratory abnormalities, drug-related uveitis, pneumonitis, bronchospasm, neurologic toxicity, hypersensitivity reactions, infusion reactions, and endocrinopathies:
 - Grade 3 drug-related uveitis, pneumonitis, bronchospasm, neurologic toxicity, hypersensitivity reaction, infusion reactions, and endocrinopathies
 - Grade 3 drug-related endocrinopathies, adequately controlled with only physiologic hormone replacement do not require discontinuation. Adrenal insufficiency requires discontinuation regardless of control with hormone replacement.
 - Grade 3 drug-related laboratory abnormalities do not require treatment discontinuation except:
 - Grade 3 drug-related thrombocytopenia > 7 days or associated with bleeding requires discontinuation
 - Grade ≥ 3 drug-related AST, ALT or Total Bilirubin requires discontinuation*
 - Concurrent AST or ALT $> 3 \times$ ULN and total bilirubin $> 2 \times$ ULN

* In most cases of Grade 3 AST or ALT elevation, study treatment will be permanently discontinued. If the investigator determines a possible favorable benefit/risk ratio that warrants continuation of study treatment, a discussion between the investigator and the BMS Medical Monitor/designee must occur.

- Any Grade 4 drug-related adverse event or laboratory abnormality, except for the following events which do not require discontinuation:
 - Grade 4 neutropenia \leq 7 days
 - Grade 4 lymphopenia or leukopenia or asymptomatic amylase or lipase
 - Isolated Grade 4 electrolyte imbalances/abnormalities that are not associated with clinical sequelae and are corrected with supplementation/appropriate management within 72 hours of their onset
 - Grade 4 drug-related endocrinopathy adverse events, such as, hyper- or hypothyroidism, or glucose intolerance, which resolve or are adequately controlled with physiologic hormone replacement (corticosteroids, thyroid hormones) or glucose-controlling agents, respectively, may not require discontinuation after discussion with and approval from the BMS Medical Monitor.

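### Protocol 4.6.2 and 4.6.4 allow resumption after Grade 2 liver abnormalities without excepting the concurrent AST/ALT-plus-bilirubin criterion that 4.6.5.1 lists for discontinuation, and the Grade 3 AST/ALT instructions also disagree

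*Protocol*

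**What the plan says.** Three adjacent protocol sections govern dosing after a liver abnormality.

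- **4.6.2 (delay).** Dosing is delayed for "Grade 2 drug-related creatinine, AST, ALT and/or Total Bilirubin abnormalities". The only pointer to discontinuation for liver tests in this section is "Grade ≥ 3 AST, ALT, total bilirubin will require dose discontinuation".
- **4.6.4 (resumption).** "Subjects with Grade 2 AST, ALT and/or Total Bilirubin Abnormalities, dosing may resume when laboratory values return to baseline", provided that any corticosteroid management is complete.
- **4.6.5.1 (discontinuation).** The list has two separate liver items: "Grade ≥ 3 drug-related AST, ALT or Total Bilirubin requires discontinuation", which carries an asterisk, and "Concurrent AST or ALT $> 3 \times$ ULN and total bilirubin $> 2 \times$ ULN", which does not. The asterisked note says that Grade 3 AST or ALT elevation leads to permanent discontinuation in most cases. It then adds an exception: "If the investigator determines a possible favorable benefit/risk ratio that warrants continuation of study treatment", the investigator must discuss it with the sponsor's Medical Monitor.

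Severity is graded by NCI CTCAE v4.0 (Table 5.1-2). The numeric grade limits are not printed in either document.

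**The concern.** The delay and resumption rules are written by grade, and their wording covers the liver tests raised singly or together. The concurrent item in 4.6.5.1 is written in multiples of ULN and states no grade. If some subjects are Grade 2 on both tests and also exceed both multiples, one part of the protocol provides for resumption and another lists the same picture for discontinuation. An investigator deciding whether to restart would naturally open 4.6.4, and nothing there points to the concurrent item.

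What is at stake is consistent handling of a liver-safety signal. Hepatotoxicity is one of the select adverse event groups in 4.6.1. The same two cut-offs also form part of the definition of potential drug-induced liver injury in 6.6. SAP 7.6.1.2 tabulates select adverse events leading to discontinuation, so those counts could depend in part on which section a site followed.

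**Working it through.** No sample size, power or event figure is involved. The check is whether any liver picture satisfies both sets of rules.

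**Step 1: general condition.** Let Grade 2 run from above a to A for AST/ALT and from above b to B for bilirubin, all in multiples of ULN. A subject is under 4.6.2 and 4.6.4 for both tests if a < AST/ALT ≤ A and b < bilirubin ≤ B, with the abnormality drug-related. The same subject meets the concurrent item if AST/ALT > 3 and bilirubin > 2. Both hold when

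- max(a, 3) < AST/ALT ≤ A, and
- max(b, 2) < bilirubin ≤ B.

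This region is non-empty whenever A > 3 and B > 2.

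**Step 2: numbers, by assumption.** Take CTCAE v4.0 Grade 2 as > 3 to 5 x ULN for AST/ALT (a = 3, A = 5) and > 1.5 to 3 x ULN for bilirubin (b = 1.5, B = 3). Then:

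- AST/ALT: max(3, 3) = 3, so the overlap is > 3 to 5 x ULN, the whole Grade 2 band.
- Bilirubin: max(1.5, 2) = 2, so the overlap is > 2 to 3 x ULN, which is (3 − 2)/(3 − 1.5) = 2/3 of the Grade 2 band.

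For example, ALT of 4 x ULN with bilirubin of 2.5 x ULN meets both sets of rules. Grade 2 bilirubin at or below 2 x ULN is not in conflict.

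**Step 3: is there a tie-breaker?** 4.6.2 points to discontinuation only from Grade 3 upwards. 4.6.4 has no exception for the concurrent item. By contrast, the rule that adrenal insufficiency requires discontinuation is stated in both 4.6.4 and 4.6.5.1. The protocol therefore repeats an override in the resumption section in one case and does not do so for the liver combination.

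**Step 4: Grade 3 and above, side by side.** This comparison needs no grade limits.

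| Finding | 4.6.2 | 4.6.5.1 item | 4.6.5.1 footnote |
|---|---|---|---|
| Grade 3 AST or ALT | Discontinuation, unqualified | Discontinuation, asterisked | Continuation possible after discussion |
| Grade 3 bilirubin | Discontinuation, unqualified | Discontinuation, asterisked | Not mentioned |
| Concurrent AST/ALT and bilirubin | Not mentioned | Listed, no asterisk | Not mentioned |

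The first row is a direct disagreement. In the other two rows the reach of the footnote is unstated: the asterisk sits on an item that includes bilirubin, but the note speaks only of AST and ALT.

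**The case against.** The strongest reply is that the sections form tiers: delay first, then conditions for resuming, then a discontinuation list that overrides both. The protocol layers Grade 2 uveitis in this way. It falls under the general delay rule for Grade 2 non-skin events, and 4.6.5.1 adds a discontinuation rule for a subset. A delay does not exclude a later stop, and 4.6.4 is permissive. This reading is reasonable, and it rules out saying that the sections necessarily command opposite actions. It does not remove the gap, because no visible text states the hierarchy.

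A reader might also infer that the concurrent item must be aimed at subjects below Grade 3, since otherwise the neighbouring Grade 3 item would make it redundant. That inference is not airtight. The neighbouring item is limited to drug-related values and carries the asterisk, while the concurrent item as printed has neither, so it could have its own effect even at Grade 3.

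The opposite inference is also tempting: that the item sits under "Grade 3 drug-related laboratory abnormalities do not require treatment discontinuation except" and so never operates below Grade 3. The indentation may have been lost when the text was extracted from PDF, so the layout cannot settle the item's scope.

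Finally, the opening of Section 4.6 is not visible, and the hepatotoxicity management guidelines are in the Investigator Brochure. A precedence rule may exist there, so the finding is limited to the text available. On the Grade 3 disagreement, the 4.6.2 line can be taken as a summary of the fuller rule in 4.6.5.1. That explains the difference in wording but still leaves an unqualified instruction beside a qualified one.

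**Conclusion.** The point stands as an inconsistency in patient-safety instructions. It has two parts. The first is an uncrossed overlap between the Grade 2 delay and resumption rules and the concurrent discontinuation item. It rests on the assumed CTCAE limits, or more generally on A > 3 and B > 2; if either condition failed, this part would fall away. The second is the disagreement over Grade 3 AST/ALT between 4.6.2 and the 4.6.5.1 footnote, which holds whatever the limits are.

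Three stronger conclusions are not supported:

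- **Permanent discontinuation for the combination.** That word appears in the footnote on Grade 3 AST/ALT, not in the concurrent item.
- **Every overlap case is potential drug-induced liver injury.** Section 6.6 also requires no initial findings of cholestasis and no other immediately apparent cause. Cases that do qualify are reported as serious events whichever dosing section a site follows.
- **The primary endpoint is distorted.** The overlap is Grade 2 by construction, while the endpoint counts high-grade events. Any effect would need re-exposure followed by a new high-grade event, and the documents give no frequency for either.

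**What to change.** Reconcile 4.6.2, 4.6.4 and 4.6.5.1 in the next amendment or a clarification letter:

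1. Cross-refer the Grade 2 liver lines in 4.6.2 and 4.6.4 to the concurrent criterion, so that the combination is assigned to one action only.
2. State the scope of that criterion: whether it applies below Grade 3, whether it is limited to drug-related values, and where it sits in the list.
3. Make the 4.6.2 line on Grade 3 or higher values and the 4.6.5.1 footnote agree, and say whether the footnote extends to bilirubin and to the concurrent criterion.

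Which action applies in each case is for the sponsor's medical team to decide. The cost is a few lines in three adjacent sections, with no new procedures or data.

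### Protocol Sections 4.6.2 and 4.6.5.1 disagree on whether a subject with Grade 3 AST or ALT may continue nivolumab, and Section 4.6.4 has no specific re-dosing criterion for one who does

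*Protocol*

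**What the plan says.** Three protocol sections bear on a drug-related Grade 3 AST or ALT elevation.

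- **Section 4.6.2 (dose delay).** One listed reason for delay is "Grade 3 drug-related laboratory abnormality, with the following exceptions". Among the exceptions beneath it stands "Grade ≥ 3 AST, ALT, total bilirubin will require dose discontinuation". That line has no asterisk, qualifier or cross-reference.
- **Section 4.6.5.1 (discontinuation).** The matching bullet reads "Grade ≥ 3 drug-related AST, ALT or Total Bilirubin requires discontinuation" and ends in an asterisk. The footnote begins "In most cases of Grade 3 AST or ALT elevation, study treatment will be permanently discontinued". It then provides that, where the investigator sees a possibly favorable balance that "warrants continuation of study treatment, a discussion between the investigator and the BMS Medical Monitor/designee must occur". It names no recovery level and no steroid condition.
- **Section 4.6.4 (resumption).** The general rule is "Subjects may resume treatment with nivolumab when the drug-related AE(s) resolve to Grade" at or below "1 or baseline value, with the following exceptions". The one liver exception is "Subjects with Grade 2 AST, ALT and/or Total Bilirubin Abnormalities, dosing may resume when laboratory values return to baseline", with the added condition that any corticosteroid management is finished. It names Grade 2 only.

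The SAP describes dosing and how delays are summarized but sets no liver-specific rule.

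**The concern.** Section 4.6.2 leaves Grade 3 or higher AST/ALT out of mandatory delay because it treats the subject as stopped. The footnote in 4.6.5.1 keeps some of those subjects on treatment. The delay and resumption sections appear to be written as if that group did not exist.

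An investigator who turns to 4.6.2 finds an instruction to stop. One who turns to 4.6.5.1 finds a route to continue. If the subject continues, neither investigator can find a criterion written for that case saying when the next dose may be given. At stake are the safety of a subject who has just had a severe liver laboratory event, and whether like cases are handled alike across a multicenter study of about 800 treated subjects.

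**Working it through.** No arithmetic applies, and the plan states no figure to reproduce. The check follows one subject, with a drug-related Grade 3 AST or ALT elevation and no other stopping criterion, through the three sections.

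**Step 1: stop or continue?** Under 4.6.2 the subject stops, without exception. Under the 4.6.5.1 footnote the subject stops in most cases and may otherwise continue. Nothing in either section says which prevails.

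**Step 2: if continued, must dosing be delayed?** The mandatory Grade 3 laboratory delay does not apply, because 4.6.2 excludes AST and ALT from it. What remains is the closing item of 4.6.2, which allows delay where the investigator judges it warranted. The Grade 2 AST/ALT delay item could apply later, if a falling value is measured at Grade 2, but not while the value is at Grade 3.

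**Step 3: when may dosing resume?** The conditions in 4.6.4 compare as follows.

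| | Laboratory condition | Steroid condition | Medical Monitor step |
|---|---|---|---|
| Grade 2 AST/ALT (liver bullet) | Baseline | Management complete, if needed | None stated |
| Grade 3 AST/ALT continued under the footnote, if the general rule applies | Grade 1 or lower, or baseline | None | Discussion (from the footnote) |
| Grade 3 AST/ALT continued under the footnote, if 4.6.4 is not reached | None stated | None | Discussion (from the footnote) |

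Any subject who meets the Grade 2 conditions also meets the general rule. The reverse fails in two cases: a value at Grade 1 but above baseline, and a value back at baseline while steroids are still being given. On the laboratory and steroid conditions, the general rule is therefore strictly weaker.

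**Step 4: how does nearby text treat similar cases?** In 4.6.4, drug-related pulmonary toxicity, diarrhea and colitis must return to baseline whatever the grade; only the liver bullet is tied to one grade. For persistent Grade 1 pneumonitis (4.6.4) and for certain Grade 4 endocrinopathies (4.6.5.1), the protocol asks for Medical Monitor approval. The footnote asks for a discussion.

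**Scope.** The footnote text names AST and ALT only, although the bullet bearing the asterisk also covers total bilirubin. Grade 4 events stay under their own rule in 4.6.5.1. The separate criterion there for combined transaminase and bilirubin elevation has no asterisk. The point is therefore confined to Grade 3 AST or ALT.

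**The case against.** The best reply is that 4.6.2 is the delay section and its AST/ALT line is only a pointer. Section 4.6.5.1 is the operative text on discontinuation, and its specific footnote qualifies the pointer. On that reading a single cross-reference would cure the conflict. This is reasonable, but the protocol does not state it, and it would leave the gap in 4.6.4 untouched.

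Second, the subject is not without protection. The footnote requires a Medical Monitor discussion that the Grade 2 rule lacks. Section 4.6.2 lets the investigator delay for any laboratory abnormality, and 4.6.5.1 ends with a stop for substantial clinical risk in the investigator's judgment. All of this stands. These are judgment steps, however, and not stated criteria for delay or recovery.

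Third, a reader might infer that the protocol deliberately sets a looser re-dosing threshold for Grade 3 than for Grade 2. The documents do not establish that. The footnote speaks of continuing treatment and never sends the subject to the general rule. The Grade 2 bullet might also be applied once a falling value is measured at Grade 2, though the text does not say so. The weaker general rule is one literal reading; the absence of any rule is another.

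Fourth, Section 4.6.1 places hepatotoxicity management guidance in the Investigator Brochure, which was not available, and parts of protocol Section 4 are not visible. The missing criterion may be there. Even so, guidance held elsewhere would not remove a disagreement between two sections of the protocol itself.

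**Conclusion.** The point holds as an inconsistency affecting patient safety and uniform conduct. Sections 4.6.2 and 4.6.5.1 give different answers on whether a Grade 3 AST or ALT subject may continue. For one who does, the visible protocol supplies no specific delay or resumption criterion. What governs re-dosing is then either the general rule or nothing stated, with the Medical Monitor discussion and the investigator-judgment items as the remaining safeguards.

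Its size cannot be expressed as a number. The documents give no rate for Grade 3 AST or ALT elevation and no indication of how often the footnote would be used. The laboratory gap between baseline and Grade 1 cannot be fixed either: the grade limits are not printed, and Section 3.3.1 admits subjects with AST and ALT up to 3 × ULN, so baseline itself varies.

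A reader might infer that the primary endpoint is biased. The documents do not support that. Section 8.4.2.1 counts subjects with a treatment-related Grade 3-4 select adverse event, by worst grade. A subject continued under the footnote has already had such an event, and later dosing cannot remove it from the count. The study is also single-arm, so no between-arm comparison is affected.

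The conclusion rests on the visible protocol text and has not been checked against the Investigator Brochure.

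**What to change.** Reconcile Sections 4.6.2, 4.6.4 and 4.6.5.1 so that they agree on two things: whether a subject with Grade 3 AST or ALT may continue and, if so, which delay and resumption criteria apply. If the exception is kept, 4.6.2 should refer to it and 4.6.4 should name the rule that governs these subjects. If it is not kept, the footnote should go. The same edit should settle whether the asterisk is meant to reach total bilirubin, and should check the result against the Investigator Brochure guidance. Which clinical rule is right is for the sponsor's clinical team.

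The cost is a wording change in the affected sections through a protocol amendment. It needs no new procedure, data collection or analysis.

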3.3.2 Exclusion Criteria

1) Target Disease Exceptions

- a) Subjects with untreated, symptomatic CNS metastases are excluded.
- b) Subjects with carcinomatous meningitis are excluded.

2) Medical History and Concurrent Diseases

- a) Subjects with active, known or suspected autoimmune disease. Subjects with Type I diabetes mellitus, residual hypothyroidism due to an autoimmune condition requiring hormone replacement, psoriasis not requiring systemic treatment, or conditions not expected to recur in the absence of an external trigger are permitted to enroll.
- b) Subjects with a condition requiring systemic treatment with either corticosteroids (> 10 mg daily prednisone equivalent) or other immunosuppressive medications within 14 days of the first dose of study drug administration. Inhaled or topical steroids and adrenal replacement steroid doses > 10 mg daily prednisone or equivalent are permitted in the absence of active autoimmune disease
- c) As of Amendment 01, this criterion is no longer applicable.
- d) Other active malignancy requiring concurrent intervention
- e) Subjects with previous malignancies (except non-melanoma skin cancers, and the following in situ cancers: bladder, gastric, colon, endometrial, cervical/dysplasia, melanoma or breast) are excluded unless a complete remission was achieved at least 2 years prior to study entry AND no additional therapy is required during the study period
- f) Any serious or uncontrolled medical disorder or active infection that, in the opinion of the investigator, may increase the risk associated with study participation, study drug administration, or would impair the ability of the subject to receive protocol therapy
- g) All toxicities attributed to prior anti-cancer therapy other than alopecia and fatigue must have resolved to Grade 1 (NCI CTCAE version 4) or baseline before administration of study drug.
- h) Subjects must have recovered from the effects of major surgery or significant traumatic injury at least 14 days before the first dose of study treatment.
- i) Known alcohol or drug abuse

- j) Subjects who received prior therapy with anti-PD-1, anti-PD-L1, anti-PD-L2, anti-CD137, or anti-CTLA-4 antibody (including ipilimumab or any other antibody or drug specifically targeting T-cell costimulation or checkpoint pathways) or who have previously taken part in a randomized BMS clinical trial for nivolumab or ipilimumab.

3) Physical and Laboratory Test Findings

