7.6.1.2 Select Adverse Events

Categories of “select AEs” have been created to group together the most common and impactful preferred terms (PTs) by organ category, providing a better estimate of the frequency of similar kinds of organ-related AEs instead of using PTs only. These select adverse events are further defined as follows:

- may differ from or be more severe than AEs caused by non-immunotherapies
- may require unique (non-standard) intervention such as immunosuppressants (or hormone replacement therapy)
- early recognition and management may mitigate severe toxicity

The preferred terms included in the ‘select AEs’ category are those that are expected to be most commonly used to describe pneumonitis, interstitial nephritis, diarrhea/colitis, hepatitis, rash, and endocrinopathies. Hypersensitivity/infusion reactions are also considered a select AE category to facilitate the pooling of the most relevant preferred terms for analyses of hypersensitivity/infusion reaction events and not because such events fit the criteria for select AEs.

Select AEs are based on the list provided by BMS every 6 months.

Unless otherwise specified, analysis will be performed by select AE category and ECOG PS group: Some analyses may also be repeated by subcategory of endocrine events.

- Overall summary of any select AEs overall and by worst CTC grade presented by Category or Subcategory/PT A presentation of by age category will also be provided. Overall summary of drug-related select AEs by worst CTC grade presented by Category or Subcategory / PT
- Overall summary of any serious select AEs by worst CTC grade presented by Category or Subcategory /PT
- Overall summary of drug-related serious select AEs by worst CTC grade presented by Category or Subcategory /PT. A presentation of by age category will also be provided.
- Overall summary of serious select Endocrine AEs by worst CTC grade presented by Category or Subcategory /PT
- Overall summary of drug-related serious select Endocrine AEs by worst CTC grade presented by Category or Subcategory /PT
- Overall summary of any select AEs leading to discontinuation overall and by worst CTC grade presented by Category or Subcategory /PT

- Overall summary of drug-related select AEs leading to discontinuation overall and by worst CTC grade presented by Category or Subcategory /PT

The analyses will be conducted using the 30-day safety window and repeated using the 100-day safety window.

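### The Grade 4 endocrinopathy exception in protocol 4.6.5.1 omits the adrenal insufficiency stop that 4.6.4 and the Grade 3 rule both carry

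*Protocol*

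**What the plan says.** Three protocol rules let a subject whose drug-related endocrinopathy is controlled on replacement therapy stay on nivolumab or go back to it.

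- **Section 4.6.4 (resumption), no grade limit.** Subjects with "drug-related endocrinopathies adequately controlled with only physiologic hormone replacement may resume treatment after consultation with the BMS Medical Monitor". The next sentence is "Adrenal insufficiency requires discontinuation regardless of control with hormone replacement".
- **Section 4.6.5.1, Grade 3.** Controlled Grade 3 endocrinopathies "do not require discontinuation. Adrenal insufficiency requires discontinuation regardless of control with hormone replacement".
- **Section 4.6.5.1, Grade 4.** The default is to stop: "Any Grade 4 drug-related adverse event or laboratory abnormality, except for the following events which do not require discontinuation". One listed exception covers Grade 4 endocrinopathies that resolve or are "adequately controlled with physiologic hormone replacement (corticosteroids, thyroid hormones) or glucose-controlling agents, respectively, may not require discontinuation". The condition is that they "may not require discontinuation after discussion with and approval from the BMS Medical Monitor". The exception ends there and does not mention adrenal insufficiency.

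On the reporting side, SAP 7.6.1.2 plans an "Overall summary of drug-related select AEs leading to discontinuation overall and by worst CTC grade".

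**The concern.** The sentence that takes adrenal insufficiency out of the permissive rule appears in two of the three places and is missing from the one that deals with the most severe events. Read alone, the Grade 4 exception only permits. Read beside the Grade 3 rule in the same section, it gives the more severe grade the more lenient treatment, and nothing in the documents explains why.

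This is a mandatory stopping rule. For a Grade 4 case controlled on steroid replacement, the Medical Monitor finds discretion to continue in 4.6.5.1 and none in 4.6.4. At stake are continued dosing in a subject whom the protocol elsewhere says must stop, and how that subject appears in the SAP table of drug-related select adverse events leading to discontinuation.

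**Working it through.** The plan gives no figure on this point, so the check is mainly a comparison of texts.

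**Step 1. The three rules side by side.**

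| Rule | Grade | Condition for staying on drug | Adrenal insufficiency stop? |
|---|---|---|---|
| 4.6.4 | Any | Controlled on physiologic replacement only; Medical Monitor (or designee) consulted | Yes |
| 4.6.5.1 | 3 | Controlled on physiologic replacement only | Yes |
| 4.6.5.1 | 4 | Resolved or controlled; Medical Monitor discussion and approval | No |

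The stop is present in 2 of 3 rules and absent from 1 of 3.

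**Step 2. Does the Grade 4 exception reach adrenal insufficiency?** It applies to endocrinopathies as a class. Thyroid disorders and glucose intolerance are given only as examples. Of the treatments it lists, thyroid hormones fit hypothyroidism and glucose-controlling agents fit glucose intolerance. Corticosteroids, described as physiologic replacement, have no obvious partner among the examples. Elsewhere the protocol links steroid replacement with the adrenal gland: exclusion criterion 2b in section 3.3.2 says that "adrenal replacement steroid doses > 10 mg daily prednisone or equivalent are permitted in the absence of active autoimmune disease". The Grade 4 wording therefore covers adrenal insufficiency without naming it.

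**Step 3. Outcome by grade, for a case controlled on replacement steroids.**

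- Grade 3: the Grade 3 rule says stop and 4.6.4 says stop. There is no ambiguity.
- Grade 4: the exception allows continuation with approval, while 4.6.4 says stop. The two conflict.

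**Step 4. Does anything set precedence?** Neither section refers to the other, and no text in the available documents ranks them. The stop is also repeated in the Grade 3 rule rather than left to 4.6.4, so a reader may take its absence at Grade 4 as deliberate.

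**Step 5. How many subjects?** The documents give no rate for adrenal insufficiency. Inputs: n = 800 treated (protocol 8.1) and an assumed Grade 4 drug-related rate of 0.05% to 0.25%. The upper end is the rare-event rate used in protocol 8.1; the lower end is purely an assumption.

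- Expected cases, n × p: 800 × 0.0005 = 0.4; 800 × 0.0025 = 2.0.
- Chance of at least one case, 1 − (1 − p)^n: 1 − 0.9995^800 = 0.330; 1 − 0.9975^800 = 0.865.

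The 86.5% differs from the 91.0% that protocol 8.1 gives for a 0.25% rate. The 91.0% corresponds to 0.3%: 1 − 0.997^800 = 0.910.

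These figures describe occurrence of a Grade 4 case, not wrongful continuation. Only resolved or controlled cases fall under the exception, so they are upper bounds. Grade 3 cases are not counted, because the rule for them is clear.

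**The case against.** The strongest reply is that both rules can be obeyed together. Section 4.6.4 is unconditional and names the condition. The Grade 4 exception is discretionary and does not. A Medical Monitor who refuses approval for adrenal insufficiency complies with both. In practice dosing would almost certainly be held during a Grade 4 adrenal event, and 4.6.4 then governs any restart. General stops also remain, in section 3.5 and at the end of 4.6.5.1, for events that make continued dosing unsafe or not in the subject's interest. Finally, the public copy does not show the introduction to section 4.6, and the management guidance sits in the Investigator Brochure, so precedence might be stated where we cannot see it.

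Much of this stands. A site cannot continue on its own reading, the default at Grade 4 is to stop, and a careful Medical Monitor would probably refuse. The case counts also rest on assumed rates and do not measure harm.

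It does not remove the conflict. That refusal satisfies both rules does not make approval acceptable: 4.6.5.1 allows approval and 4.6.4 leaves no room for it. Treating 4.6.4 as a second gate after a hold is sensible, but the protocol does not say so, and its title confines it to resumption while 4.6.5.1 is the dedicated list of discontinuation rules. That unseen text settles the matter is speculation.

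**Conclusion.** The concern holds. One of the three permissive endocrinopathy rules lacks the adrenal insufficiency stop, and at Grade 4 that puts 4.6.5.1 in conflict with 4.6.4. The likeliest cause is a drafting omission, though the documents cannot show intent.

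The conflict is a matter of text and does not depend on any rate. Its reach is narrow: under the assumed rates, at most about 0.4 to 2 subjects of 800. The primary endpoint incidence, the sample size and the efficacy estimates are unaffected. The possible effects are on dosing safety in those few subjects and on the count in one descriptive table. It should be fixed because it is a mandatory safety rule and the correction is almost free.

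**What to change.** At the end of the Grade 4 endocrinopathy exception in 4.6.5.1, add the sentence already used in the other two places: "Adrenal insufficiency requires discontinuation regardless of control with hormone replacement". If the sponsor's safety team does intend to allow continuation with Medical Monitor approval, amend 4.6.4 and the Grade 3 rule instead, so that all three agree.

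The cost is one sentence in the next protocol revision and a short letter to sites. No new procedures, data or patients are needed.
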